10.2 Safety

10.2.1 Evaluations

Safety and tolerability will be evaluated by solicited local and systemic AEs (immediate AEs within 30 minutes post-vaccination and solicited AEs up to seven days post-vaccination), unsolicited AEs up to 28 days post-vaccination (including immediate unsolicited AEs within 30 minutes post-vaccination), and SAEs, AESIs, MAAEs, NOCDs, and AEs leading to withdrawal up to the end of the study. In addition, events will be monitored for a possible hypersensitivity component and potential immune-mediated diseases from all reported events during the study (collected AEs, SAEs, AESIs, NOCDs, and AEs leading to withdrawal). Clinical safety methods will include repeated urine, blood chemistry and haematology testing.

10.2.1.1 Solicited Local and Systemic AEs

Subjects will be monitored for both solicited local AEs (erythema, swelling, and pain at the injection site) and solicited systemic AEs (fever, headache, fatigue, muscle aches, joint aches, chills, a feeling of general discomfort, swelling in the axilla, and swelling in the neck) from the time of vaccination through Day 7. While the subjects remain in the clinic following vaccine administration (at least 30 minutes), staff will monitor them for local and systemic AEs; after release from the clinic facility, from the evening of Day 0 to the evening of Day 7, subjects will measure and record their local and systemic AEs in their diary.

The intensity of the solicited local and systemic AEs will be assessed by the subject, documented in the diary, and graded as: mild (1), moderate (2), severe (3) or potentially life threatening (4) (please refer to Table 6). The causal relationship of all solicited local and systemic AEs will be considered related.

The Investigator should assess solicited AEs and determine if any meet the criteria for SAE. Any solicited local or systemic AEs that meet the criteria for SAE should be reported to the Sponsor within 24 hours (Section 13.1.6) and entered as an SAE in the eCRF.

Table 6 Severity Grades for Solicited Local and Systemic AEs

Symptoms	Severity								
	None Gr.		Grade 2 (Moderate)	Grade 3 (Severe)	Grade 4 (Potentially life- threatening)				
Injection Site AEs (Lo	cal AEs)		1		•				
Erythema (redness)	< 25 mm	25 - 50 mm	51 - 100 mm	> 100 mm	Necrosis or exfoliative dermatitis				
Swelling	< 25 mm	25 - 50 mm and does not interfere with activity	51 – 100 mm or interferes with activity	> 100 mm or prevents daily activity	Necrosis				
Pain	None	Does not interfere with activity	Repeated use of non-narcotic pain reliever for more than 24 hours or interferes with activity	Any use of narcotic pain reliever or prevents daily activity	Results in a visit to emergency room (ER) or hospitalization				
Solicited Systemic AE	S								
Fever (°C or °F)	< 38.0 °C < 100.4 °F	38.0 - 38.4 °C 100.4 - 101.1 °F	38.5 - 38.9 °C 101.2 - 102.0 °F	39.0 - 40.0 °C 102.1 - 104.0 °F	> 40.0 °C > 104.0 °F				
Headache	None	No interference with activity	Repeated use of non-narcotic pain reliever for more than 24 hours or some interference with activity	Significant; any use of narcotic pain reliever or prevents daily activity	Results in a visit to emergency room (ER) or hospitalization				
Fatigue	None	No interference with activity	Some interference with activity	Significant; prevents daily activity	Results in a visit to emergency room (ER) or hospitalization				
Muscle aches	None	No interference with activity	Some interference with activity	Significant; prevents daily activity	Results in a visit to emergency room (ER) or hospitalization				
Joint aches, chills, feeling of general discomfort or uneasiness (malaise), swelling in the axilla, swelling in the neck	None	No interference with activity	Some interference with activity not requiring medical intervention	Prevents daily activity and requires medical intervention	Results in a visit to emergency room (ER) or hospitalization				

10.2.1.2 Adverse Events

All spontaneous unsolicited AEs occurring within 28 days after vaccination will be reported in the "Adverse Event" screen in the subject's eCRF, irrespective of intensity or whether or not they are considered to be vaccination-related. Thereafter, from Day 29 to the end of the study, SAEs, AEs leading to withdrawal, AESIs, and NOCDs will be monitored and reported in the eCRF.

The intensity of unsolicited AEs will be graded as: mild (1), moderate (2), severe (3) or potentially life threatening (4), according to the FDA Guidance for Industry [FDA 2007]. Their causal relationship with the study vaccine will be assessed by the Investigator (definitely not related, probably not related, possibly related, probably related or definitely related); see Section 13.1.9 for a definition of these causal relationships.

The Investigator should assess unsolicited AEs and determine if any meet the criteria for SAE. Any unsolicited AEs that meet the criteria for SAE should be reported to the Sponsor within 24 hours (Section 13.1.6) and entered as an SAE in the eCRF.

10.2.1.3 Clinical Laboratory Tests

Blood samples for biochemistry and haematology, HIV, Hepatitis B and Hepatitis C markers in serum, and urine samples for urinalysis will be collected according to the Time and Events Schedule (see Table 1). Any laboratory result outside of the testing laboratory's normal range will be classified as 'clinically significant' (CS) or 'not clinically significant' (NCS) by the site Investigator, with appropriate documentation. Any laboratory test performed at screening with a value outside the normal range may be repeated (prior to vaccination) at the discretion of the Investigator. Repeated tests will be considered the Baseline results.

The Investigator must review the laboratory reports, document this review, and record any clinically relevant changes occurring during the study in the source documents. The tests to be performed by the laboratory are presented in Table 7.

Table 7 Clinical Laboratory Tests

Biochemistry (serum):		
Sodium	Alkaline phosphatase	
Potassium	Alanine transferase (ALT)	
Urea	Aspartate transferase (AST)	
Creatinine	Gamma glutamyltransferase (GGT)	
Glucose	Cholesterol (total, HDL, LDL)	
Bilirubin (total)	Triglyceride	
Albumin	Chloride	
Total protein	Calcium	
	Phosphorus	
Haematology:		
Haemoglobin	Mean cell haemoglobin (MCH)	
Hematocrit	Mean cell concentration (MCHC)	
Red blood cells	Mean cell volume (MCV)	
Platelets	Lymphocytes	
Mean platelet volume (MPV)	Monocytes	
White cell count (total, WBC)	Eosinophils	
Neutrophils	Basophils	

Serology:		
HIV	Hepatitis B	
Hepatitis C		
Urinalysis:		
Macroscopic examination (color, aspect)	Glucose	
рН	Protein	
Specific gravity	Blood	

All protocol required safety laboratory parameters are defined in study-specific documentation.

10.2.1.4 Vital Signs

Vital signs measurements (resting BP, HR, and OT) will be performed as part of screening procedures (prior to eligibility assessment on Day 0) and after the post-vaccination surveillance period.

OT will be collected in degrees Celsius or Fahrenheit using a digital thermometer by the Sponsor. The OT measurement should not be collected immediately following consumption of a hot or cold beverage or after smoking.

BP will be taken after the subject has been in a seated position as per the site's standard procedure. BP should be taken by cuff (manual or automated are both acceptable). BP and HR may be repeated once if judged necessary. All measurements (including any repeats) will be recorded in the source documents.

10.2.1.5 Physical Examinations

A limited physical examination will be performed by the Investigator (or sub-Investigator) as part of screening procedures and on Day 0 (prior to eligibility assessment) and Day 3. History/symptom-directed physical examinations may be performed at any other study visits if 1) new complaints or concerns are raised by either the study subject or study staff and 2) deemed to be necessary by the Investigator.

10.2.2 Safety Endpoints

10.2.2.1 Primary Endpoints

- Occurrences, intensity, and relationship to vaccination of immediate AEs (30 minutes post-vaccination);
- Occurrences and intensity of solicited local and systemic AEs (for seven days following study vaccine administration);
- Occurrences, intensity, and relationship of unsolicited AEs for 28 days following study vaccine administration;
- Number and percentage of subjects with normal and abnormal, clinically significant urine, haematological and blood biochemistry values, and urinalysis at Days 0, 3, and 28;

- Occurrences of SAEs, AEs leading to withdrawal, AESIs, MAAEs, NOCDs, and deaths up to Day 28;
- Occurrences of SAEs, AEs leading to withdrawal, AESIs, MAAEs, NOCDs, and deaths from Day 29 up to Day 182;
- Occurrences of SAEs, AEs leading to withdrawal, AESIs, MAAEs, NOCDs, and deaths from Day 183 up to the end of the study (Day 365).

10.2.2.2 Secondary Endpoints

- Occurrences, intensity, and relationship to vaccination of immediate AEs (30 minutes post-vaccination), stratified by prior influenza vaccination status, if >25% of the enrolled subjects have received a standard influenza vaccine during the 12 months prior to study vaccination;
- Occurrences and intensity of solicited local and systemic AEs (for seven days following study vaccine administration), stratified by prior influenza vaccination status, if >25% of the enrolled subjects have received a standard influenza vaccine during the 12 months prior to study vaccination;
- Occurrences, intensity, and relationship of unsolicited AEs for 28 days following study vaccine administration, stratified by prior influenza vaccination status, if >25% of the enrolled subjects have received a standard influenza vaccine during the 12 months prior to study vaccination;
- Number and percentage of subjects with normal and abnormal, clinically significant urine, haematological and blood biochemistry values, and urinalysis at Days 0, 3, and 28, stratified by prior influenza vaccination status, if >25% of the enrolled subjects have received a standard influenza vaccine during the 12 months prior to study vaccination;
- Occurrences of SAEs, AEs leading to withdrawal, AESIs, MAAEs, NOCDs, and deaths up to Day 28, stratified by prior influenza vaccination status, if >25% of the enrolled subjects have received a standard influenza vaccine during the 12 months prior to study vaccination;
- Occurrences of SAEs, AEs leading to withdrawal, AESIs, MAAEs, NOCDs, and deaths from Day 29 up to Day 182, stratified by prior influenza vaccination status, if >25% of the enrolled subjects have received a standard influenza vaccine during the 12 months prior to study vaccination;
- Occurrences of SAEs, AEs leading to withdrawal, AESIs, MAAEs, NOCDs, and deaths from Day 183 up to the end of the study (Day 365), stratified by prior influenza vaccination status, if >25% of the enrolled subjects have received a standard influenza vaccine during the 12 months prior to study vaccination.

10.3 Immunogenicity

10.3.1 Immunogenicity Evaluations

Immunogenicity will be evaluated by the humoral immune response induced in subjects, using the HI assay on Days 0, 28, 182, and 365 and using the MN assay on Days 0 and 28.

The blood samples for immunogenicity will be analyzed in one or more central laboratories; information on processing and the central laboratories will be provided in the study-specific documentation.

10.3.2 Immunogenicity Endpoints

Unless otherwise mentioned, point estimates and 95 % CI will be calculated for all immunogenicity endpoints and responses in the adjuvanted QVLP recipients will be compared with the active comparator groups using descriptive statistics.

10.3.2.1 Primary Endpoint

- HI antibody response induced by adjuvanted and unadjuvanted QVLP and Fluzone HD Quad against the homologous influenza strains on Day 28, compared to Day 0 values, will be analyzed as follows:
 - GMTs of HI antibody on Days 0 and 28;
 - SC rate: the proportion of subjects in a given treatment group with either a ≥ 4-fold increase in reciprocal HI titers between Day 0 and Day 28 or a rise of undetectable HI titer (i.e. < 10) pre-vaccination (Day 0) to an HI titer of ≥ 40 on Day 28;
 - SP rate: the proportion of subjects in a given treatment group attaining a reciprocal HI titer of ≥ 40 on Day 28 (the percentage of vaccine recipients with a serum HI titer of at least 1:40 following vaccination);
 - GMFR: the geometric mean of the ratio of GMTs (Day 28/Day 0).

10.3.2.2 Secondary Endpoints

- MN antibody response induced by adjuvanted and unadjuvanted QVLP and Fluzone HD Quad against the homologous influenza strains on Day 28, compared to Day 0 values, will be analyzed as follows:
 - GMTs of MN antibody on Days 0 and 28;
 - SC rate: the proportion of subjects in a given treatment group with either a ≥ 4-fold increase in reciprocal MN titers between Day 0 and Day 28 or a rise of undetectable MN titer (i.e. 7.1) pre-vaccination (Day 0) to an MN titer of ≥ 28.3 at Day 28 post-vaccination;
 - GMFR: the geometric mean of the ratio of GMTs (Day 28/Day 0).

- HI antibody response induced by adjuvanted and unadjuvanted QVLP and Fluzone HD
 Quad against the heterologous influenza strains on Day 28, compared to Day 0 values. HI
 antibody titers will be analyzed as follows:
 - GMTs of HI antibody on Days 0 and 28;
 - SC rate: the proportion of subjects in a given treatment group with either a ≥ 4-fold increase in reciprocal HI titers between Day 0 and Day 28 or a rise of undetectable HI titer (i.e. < 10) pre-vaccination (Day 0) to an HI titer of ≥ 40 on Day 28;
 - SP rate: the proportion of subjects in a given treatment group attaining a reciprocal HI titer of ≥ 40 on Day 28 (the percentage of vaccine recipients with a serum HI titer of at least 1:40 following vaccination);
 - GMFR: the geometric mean of the ratio of GMTs (Day 28/Day 0).
- HI antibody response (against homologous and heterologous influenza strains) and MN antibody response (against homologous influenza strains) induced by adjuvanted and unadjuvanted QVLP and Fluzone HD Quad on Day 28, compared to Day 0 values, stratified by prior influenza vaccination status, if >25% of the enrolled subjects have received a standard influenza vaccine during the 12 months prior to study vaccination;
- Durability of antibody responses 6 months post-vaccination, as determined by HI antibody responses induced by adjuvanted and unadjuvanted QVLP and Fluzone HD Quad against the homologous influenza strains on Day 182, compared to Day 0 values.
 - HI antibody titers will be analyzed as follows:
 - GMTs of HI antibody on Day 182;
 - SC rate: the proportion of subjects in a given treatment group with either a ≥ 4-fold increase in reciprocal HI titers between Day 0 and Day 182 or a rise of undetectable HI titer (i.e. < 10) pre-vaccination (Day 0) to an HI titer of ≥ 40 on Day 182;
 - SP rate: the proportion of subjects in a given treatment group attaining a reciprocal HI titer of ≥ 40 on Day 182 (the percentage of vaccine recipients with a serum HI titer of at least 1:40 following vaccination);
 - GMFR: the geometric mean of the ratio of GMTs (Day 182/Day 0).
- Durability of antibody responses 12 months post-vaccination, as determined by HI antibody responses induced by adjuvanted and unadjuvanted QVLP and Fluzone HD Quad against the homologous influenza strains on Day 365, compared to Day 0 values.
 - HI antibody titers will be analyzed as follows:
 - GMTs of HI antibody on Day 365;
 - SC rate: the proportion of subjects in a given treatment group with either a ≥ 4-fold increase in reciprocal HI titers between Day 0 and Day 365 or a rise of undetectable HI titer (i.e. < 10) pre-vaccination (Day 0) to an HI titer of ≥ 40 on Day 365;
 - SP rate: the proportion of subjects in a given treatment group attaining a reciprocal HI titer of ≥ 40 on Day 365 (the percentage of vaccine recipients with a serum HI titer of at least 1:40 following vaccination);

• GMFR: the geometric mean of the ratio of GMTs (Day 365/Day 0);

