# 4.1. Sample Size

No statistical sample size calculations were performed. The determined sample size up to approximately 120 subjects with 40 subjects in each treatment group will make it possible to perform the initial evaluation of vaccine immunogenicity and detect sizable differences in rates of adverse events since objective of this study is to quantify the type, percentage, intensity, duration, and relationship of common post-vaccination safety events to determine if they differ clinically among the treatment groups.

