# 8.1. Primary Immunogenicity Analysis

The primary immunogenicity analysis endpoint is to evaluate the HI antibody response induced by adjuvanted and unadjuvanted QVLP and Fluzone HD Quad against the homologous influenza strains on Day 28, compared to Day 0 values, analyzed as follows:

- GMT at Day 0 and Day 28;
- SC rate at Day 28: the proportion of subjects in a given treatment group with either a ≥ 4-fold increase in reciprocal HI titers between Day 0 and Day 28 or a rise of undetectable HI titer (i.e., < 10) pre-vaccination (Day 0) to an HI titer of ≥ 40 on Day 28:
- SP rate at Day 28: the proportion of subjects in a given treatment group attaining a reciprocal HI titer of ≥ 40 on Day 28 (the percentage of vaccine recipients with a serum HI titer of at least 1:40 following vaccination);
- GMFR (Day 28/Day 0): the geometric mean of the ratio of GMTs (Day 28/Day 0).

For the H1 and H3 analysis, results from the assay using VLP reagents will be used. Any antibody titer that is below the LLOQ of assay will be imputed with a value equal to half of the LLOQ of assay of the antigen specific antibody titer.

GMT will be calculated as anti-logarithm of ( $\sum$ (log-transformed titer)/number of subjects with titer information). The 95% CI for GMT will be calculated as the anti-log transformation of upper and lower limits for a 2-sided CI of the mean of the log-transformed titers. The log-transformed GMT will be compared among treatment groups by using the analysis of variance (ANOVA) model on log-transformed titer values and the Tukey's test will also be performed for the pairwise comparisons between treatment groups within the frame of the same model.

The point estimates and the corresponding two-sided 95 % Clopper-Pearson CI [Clopper, 1934] for subjects achieving SC and SP will be calculated and compared among treatment groups using Fisher's exact test.

GMFR will be calculated as anti-logarithm of  $\sum$  [log-transformed titer ratio of Yi/Bi)/number of subjects with titer information], where Yi is the post-vaccination titer and Bi is the pre-vaccination (baseline) titer for subject i. The 95% CI for GMFR will be calculated as the anti-log transformation of upper and lower limits for a 2-sided CI of the mean of the log-transformed titers fold rise from pre-vaccination. The log-transformed

Medicago USA Page **32** of **55** 

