### 8.2. Secondary Immunogenicity Analysis

The secondary immunogenicity analysis endpoints include the following evaluations:

- MN antibody response induced by adjuvanted and unadjuvanted QVLP and Fluzone HD
  Quad against the homologous influenza strains on Day 28, compared to Day 0 values,
  which will be analyzed as follows:
  - O GMT at Days 0 and Day 28;
  - SC rate at Day 28: the proportion of subjects in a given treatment group with either  $a \ge 4$ -fold increase in reciprocal MN titers between Day 0 and Day 28 or a rise of undetectable MN titer (i.e., 7.1) pre-vaccination (Day 0) to an MN titer of  $\ge 28.3$  at Day 28 post-vaccination;
  - o GMFR (Day 28/Day 0): the geometric mean of the ratio of GMTs.

These analyses will be repeated but by prior influenza vaccination status, if >25% of the enrolled subjects have received a standard influenza vaccine during the 12 months prior to study vaccination.

- HI antibody response induced by adjuvanted and unadjuvanted QVLP and Fluzone HD Quad against the heterologous influenza strains on Day 28, compared to Day 0 values. The same summaries will be provided as primary analysis.
  - GMT at Day 0 and Day 28;
  - o SC rate at Day 28;
  - o SP rate at Day 28;
  - GMFR (Day 28/Day 0).

These analyses will be repeated but by prior influenza vaccination status, if >25% of the enrolled subjects have received a standard influenza vaccine during the 12 months prior to study vaccination.

- HI antibody response induced by adjuvanted and unadjuvanted QVLP and Fluzone HD Quad against the homologous influenza strains on Day 28, compared to Day 0 values by prior influenza vaccination status, if >25% of the enrolled subjects have received a standard influenza vaccine during the 12 months prior to study vaccination. The same summaries will be provided as primary analysis.
  - o GMT at Day 0 and Day 28;
  - o SC rate at Day 28;
  - o SP rate at Day 28;
  - GMFR (Day 28/Day 0).

Confidential

Medicago USA Page 33 of 55

- Durability of antibody responses 6 months (Day 182) and 12 months (Day 365) post-vaccination determined by HI antibody responses.
  - o HI antibody titers will be analyzed as follows:
    - o GMT at Day 182 and Day 365;
    - o SC rate at Day 182 and Day 365;
    - o SP rate at Day 182 and Day 365;
    - o GMFR (Day 182/Day 0 and Day 365/Day 0).

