# To calculate adjusted GMFR and do the ANCOVA:

PROC MIXED data=tab(where=(avisitn = Day <0, 28, 182, 365>)); \*\* to be repeated for each relevant timepoints

BY STRAIN;

CLASS TRT:

MODEL var = TRT BASE; \*\* where var=LOG10(Analysis value/Baseline value) and BASE is LOG10(Baseline value)

LSMEANS TRT / DIFF=ALL CL ALPHA=0.05 ADJUST=tukey;

RUN;

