#### Analysis of SC/SP

• 95% CI

PROC FREQ data=tab;

BY STRAIN TRT;

TABLE var / binomial (exact); \*\* where var=Subject achieving SC or SP

RUN:

• Fisher's Exact Test:

PROC FREQ data=tab;

BY STRAIN;

TABLE var\*TRT/ fisher; \*\* where var=Subject achieving SC or SP

RUN:

Note: The MN assay will be performed on Day 0 and Day 28 only, and not on Day 182 and Day 365.

Confidential

Medicago USA Page 48 of 55

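### If MN titers are held to one decimal, the literal ≥ 4-fold limb would miss exact two-dilution rises from some detectable baselines and understate the secondary MN seroconversion rate

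*Protocol*

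**What the plan says.** Protocol 10.3.2.2 defines MN seroconversion by two alternatives. The first is "either a ≥ 4-fold increase in reciprocal MN titers between Day 0 and Day 28". The second is a rise from "undetectable MN titer (i.e. 7.1) pre-vaccination (Day 0) to an MN titer of ≥ 28.3 at Day 28 post-vaccination". SAP 8.2 repeats the rule, again giving the undetectable level as a single value: "undetectable MN titer (i.e., 7.1) pre-vaccination (Day 0) to an MN titer of" at least 28.3.

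SAP 8.1 adds a rule for low titers: "Any antibody titer that is below the LLOQ of assay will be imputed with a value equal to half of the LLOQ". The LLOQ of the MN assay is not given. The GMFR code in SAP Appendix 13.3 works on a ratio of stored values ("where var=LOG10(Analysis value/Baseline value) and BASE is LOG10(Baseline value"). The seroconversion code takes a ready-made yes/no flag ("where var=Subject achieving SC or SP") and does not show how the flag is derived.

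For HI, the corresponding rule in Protocol 10.3.2.1 reads "undetectable HI titer (i.e. < 10) pre-vaccination (Day 0) to an HI titer of ≥ 40 on Day 28".

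Neither document states the MN dilution series, the number of decimals at which titers are reported or stored, how replicate readings are combined, or any tolerance for the 4-fold comparison.

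**The concern.** On a two-fold dilution scale, a 4-fold rise is two dilution steps. If the titers on that scale are irrational numbers rounded to one decimal, the ratio of two rounded values two steps apart is not exactly 4. It falls just above or just below, depending on how the two values happened to round. A strict comparison with 4 then treats the same biological response differently according to the baseline.

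Two features of the text suggest that the data may be held to one decimal. HI undetectable is given as a range, below 10, while MN undetectable is given as the single value 7.1, which reads like a recorded data value. Also, the unrounded titer two steps above 5√2 is 28.284, which is below the printed cut-off of 28.3, so the second limb works as written only on rounded titers.

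At stake is the MN seroconversion rate, a named secondary parameter. SAP 8.2 applies the primary-endpoint methods to it, so it is compared among groups by Fisher's exact test. A shortfall could differ between groups if their baselines, or their shares of exact two-step rises, differ.

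**Working it through.** **Inputs from the documents.** The 4-fold limb; the 7.1 to ≥ 28.3 limb; LLOQ/2 imputation; 40 subjects per group.

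**Assumptions, not in the documents.** MN titers lie on the grid 5√2 × 2^k, are stored to one decimal, and are compared strictly with 4.

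**Reproducing the printed values.** 5√2 = 7.0711, which rounds to 7.1. 20√2 = 28.2843, which rounds to 28.3. The exact ratio is 4; the printed ratio is 28.3/7.1 = 3.986.

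**Two-dilution rises on the one-decimal grid**

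| Day 0 | Day 28 | Ratio | ≥ 4-fold limb | Counted by either limb |
|---|---|---|---|---|
| 7.1 | 28.3 | 3.9859 | no | yes (second limb) |
| 14.1 | 56.6 | 4.0142 | yes | yes |
| 28.3 | 113.1 | 3.9965 | no | **no** |
| 56.6 | 226.3 | 3.9982 | no | **no** |
| 113.1 | 452.5 | 4.0009 | yes | yes |
| 226.3 | 905.1 | 3.9996 | no | **no** |
| 452.5 | 1810.2 | 4.0004 | yes | yes |

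Higher up the grid, baselines 905.1 and 1810.2 pass and 3620.4 fails (14481.5/3620.4 = 3.99997).

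**Direction.** The largest one-step ratio is 28.3/14.1 = 2.007 and the smallest three-step ratio is 56.6/7.1 = 7.97. No smaller rise is wrongly admitted and no larger rise is lost, so the error can only lower the rate.

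**Other precisions.** At full precision every two-step ratio is 4.0 and nothing is lost. Storing two or three decimals does not fully cure the problem: for example 226.27/56.57 = 3.9998 and 226.274/56.569 = 3.99996.

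**Size under the one-decimal assumption.** Loss = (share of subjects at affected baselines) × (chance of an exactly two-step rise among them). The documents give neither input.
- 20% × 10% = 2 percentage points, or 0.8 of 40 subjects.
- 40% × 20% = 8 percentage points, or 3.2 of 40.
- 60% × 30% = 18 percentage points, or 7.2 of 40.

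**LLOQ/2 imputation.** An LLOQ of 14.1 gives 7.05, and an LLOQ of 7.1 gives 3.55. Neither equals 7.1, so a second limb coded as baseline = 7.1 would not fire. A Day 28 titer of 28.3 would still pass the first limb (28.3/7.05 = 4.014; 28.3/3.55 = 7.97).

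**HI for comparison.** On a 5/10/20/40 scale (assumed from the printed 10 and 40), every two-step ratio is exactly 4.

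**The case against.** The only pair the documents print, 7.1 to 28.3, causes no harm. A reader might infer from 28.3/7.1 = 3.99 that the plan contradicts itself or loses subjects with undetectable baselines. It does not: the limbs are alternatives, and the second counts that pair explicitly.

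A reader might also take it as fact that the rule understates MN seroconversion. The documents do not support that either. It needs the √2 grid, one-decimal storage and a strict comparison together, and none of these is stated. Rounding only for display fits the printed numbers too. In that case the 28.284 titer misses the literal 28.3 cut-off, but the first limb counts the pair at a ratio of exactly 4. Laboratory detail is left to study-specific documentation (Protocol 10.3.1), and the flag derivation is not shown.

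Nor can a definite loss be quoted. A simulation with assumed baseline and rise distributions gave 9 to 18 points, but those distributions are not in the documents. If each titer were the geometric mean of two readings, also an assumption, a similar simulation gave about 2 to 5 points.

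Finally, the reach is small. MN GMT and GMFR are practically unaffected by one-decimal rounding, and the study was not sized on this rate ("No statistical sample size calculations were performed").

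All of this stands, and it limits the point to a conditional one. What it does not remove is that the rule, applied literally to values at the precision the plan prints, gives a wrong answer in one direction, and that nothing in the SAP prevents that application.

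**Conclusion.** The point holds conditionally. On one-decimal titers with a strict comparison, exact two-dilution rises from 28.3, 56.6 and 226.3 would be counted as non-response, while the same rise from 14.1, 113.1 or 452.5 would count as response. The MN seroconversion rate would be understated, never overstated.

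The size cannot be determined from the documents. It is zero with unrounded titers. With one-decimal titers it is about 2 to 18 percentage points for the assumed shares above, or about 1 to 7 of 40 subjects per group.

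The primary HI endpoint is outside the problem on a 10/20/40 scale. This is a low-priority improvement to a secondary endpoint that costs almost nothing.

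**What to change.** In SAP 8.2:

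1. Derive the MN 4-fold limb from unrounded titers. Where only one-decimal titers are available, define it as a rise of at least two doubling dilutions, for example round(log2(Day 28/Day 0), 2) ≥ 2.00. The three affected rises then pass: log2 of 3.9965, 3.9982 and 3.9996 is 1.9987, 1.9994 and 1.9998, each rounding to 2.00.
2. Keep the separate undetectable-to-≥ 28.3 limb unchanged. It is still needed, because log2(28.3/7.1) = 1.9949 rounds to 1.99.
3. State the MN LLOQ and the stored titer precision, so that the LLOQ/2 imputation agrees with the 7.1 used as the undetectable value.

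Two decimals in the rounding matter. Rounding log2 to one decimal would admit ratios from about 3.86. It would also admit 14.1/3.55 = 3.97 if the LLOQ were 7.1, although 14.1 is below the plan's 28.3 cut-off. The two-decimal rule starts at 2^1.995 = 3.986 and rejects that case (log2 = 1.990).

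The cost is a sentence or two in the SAP and one line of derivation code. On the assumed grid at one decimal or finer, the flag changes only where rounding would have misclassified a subject.
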